7.10 Efficacy Assessments

7.10.1 Clinical Worsening

Clinical worsening will be assessed from randomization to the first of the following events:

To compare the effects of BPS-314*d*-MR to placebo in patients receiving inhaled treprostinil (Tyvaso®) on time-to-clinical-worsening (TtCW) defined as the time from randomization to the first of any of the following clinical worsening events:

- Death (all causes)
- Hospitalization due to worsening PAH defined as:
 - Non-elective hospitalization lasting at least 24 hours in duration caused by clinical conditions directly related to PAH and/or right heart failure and requiring intensification of treatment; or
 - Lung or heart / lung transplantation; or
 - Atrial septostomy
- Initiation of a parenteral (infusion or sub-cutaneous) prostacyclin, directly related to worsening PAH (transient use [≤ 7 days] for non-PAH related illness allowable)
- Disease progression (all criteria required):
 - A decrease in six minute walk distance (6MWD) of at least 15% from Baseline (defined as the average of the two 6MWTs performed on sequential days of the Baseline Visit), or being too ill to walk as a consequence of PAH progression, confirmed by six-minute walk tests (6MWT) performed at 2 consecutive visits

- Worsening of PAH symptoms, which must include either:
 - An increase in WHO Functional Class or
 - Worsening symptoms of right heart failure
- Unsatisfactory long-term clinical response (all criteria below required):
 - Receiving randomized treatment for at least 24 weeks
 - A decrease of at least 15% from Baseline (defined as the average of the two Baseline Visit 6MWTs) in 6MWD, or too ill to walk, directly related to PAH progression, at Week 24 and beyond; at 2 consecutive visits, and
 - Sustained WHO Functional Class III or IV symptoms for at least 24 weeks.

The Investigator will initially judge whether a suspected clinical worsening event has occurred based on the definition provided above. An EAC will be established by the Sponsor to review all suspected clinical worsening events and make a final determination. The Committee will be composed of medical experts in the PAH field, will be independent from the Sponsor, and will assess each event in a blinded fashion. Specific details regarding the Committee's membership, processes and procedures will be outlined in the EAC charter.

Subjects will continue their participation in the study until a clinical worsening event is confirmed by the EAC or the study is formally concluded by the Sponsor.

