Subjects will continue participation in the study until it is formally concluded by the Sponsor. Subjects are expected to remain on study drug throughout their participation in the study unless/until IV or SQ prostanoid therapy is added or in the event of lung transplantation. If a subject discontinues the study for any reason prior to the formal conclusion of the study by the Sponsor, the subject will be asked to return to the clinical for an End of Study (Early Termination) Visit. Vital status will be assessed for all randomized subjects at the formal conclusion of the study. For randomized subjects who terminate early, vital status will be assessed three months following discontinuation unless the formal conclusion of the study occurs within the three month time period.

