Following the Baseline Visit, subjects will return to the study site for scheduled study visits at Week 4, Week 8, and Week 12 (first Quarterly Visit) and for scheduled Quarterly Visits thereafter. Subjects will undergo all scheduled efficacy and safety assessments as defined by the protocol and the Schedule of Events (Appendix 1). Between scheduled study visits, the subject will be contacted to assess for possible clinical worsening events and to record any newly occurring or changes to adverse events or concomitant medications. Subject contact should occur weekly for the first twelve weeks (except for study visit weeks) when subjects are becoming familiar with the study drug dosing (including up-titration to the fixed dose, as tolerated) and study procedures. Subjects should be contacted monthly between scheduled Quarterly Visits through the end of study participation.

Subjects will continue the study until it is formally concluded by the Sponsor. Following study conclusion the subject will return to the clinical site for an End of Study Visit to undergo all scheduled assessments. Subjects who are participating in the study at its conclusion may be offered the opportunity to enroll in a long-term open-label extension study.

In the event that a subject withdraws consent for participation in the study or the Investigator terminates the subject from the study the subject will be weaned from study drug and will return to the clinical site for an End of Study (Early Termination) Visit to undergo all scheduled assessments.

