7.10.2 Clinical Failure

Clinical failure will be assessed from randomization to the first of the following events:

- Meets primary endpoint definition of clinical worsening, as confirmed by EAC, or
- Receives randomized treatment for at least 24 weeks and has:
 - Lack of sustained improvement from Baseline WHO Functional Class: defined by two consecutive visits of no sustained improvement from Baseline WHO FC, visits may be scheduled or unscheduled; and
 - Lack of sustained improvement from Baseline 6MWD (average at Baseline): defined by two consecutive visits of no sustained improvement from Baseline 6MWD (≤ 0 meters or too ill to walk, directly related to PAH), visits may be scheduled or unscheduled.

The Sponsor will derive the composite measures of clinical failure and TtCF from the data collected per the protocol. Unlike clinical worsening, neither a specific Investigator's assessment for clinical failure nor an EAC confirmation of suspected events will occur.

As above, subjects are expected to continue their participation in the study until a clinical worsening event is confirmed by the EAC or the study is formally concluded by the Sponsor.

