6.4.2 Handling of Missing Data

The sponsor acknowledges the implications of missing data on the integrity of study outcomes and, consistent with Fleming's recommendations (2011), implemented the following strategies to minimize the extent of missing data:

1. All subjects were allowed to continue in the study until the close of study, whether on IMP or not. Subjects were not to be summarily discontinued from the study, unless 1) the subject withdrew informed consent; 2) the subject met a primary endpoint and declined continuation in the study; or 3) the subject continued to be non-adherent to study protocol after repeated attempts to correct (at least 6 months). However, the subject has the right to discontinue from the study at any time. All subjects who discontinue the study, unless they withdraw informed consent, will continue to be followed, to the extent possible, for vital status until the sponsor concludes the study.
2. Recent publications (Sitbon et al., 2015; Galiè et al., 2015) have shown that roughly 20% of subjects prematurely terminate from mortality and morbidity studies in PAH. The sponsor has throughout the study engaged with study investigators to encourage subjects' retention in the study, adherence with the protocol, and compliance with IMP.
3. While the study protocol is necessarily complex in order to obtain the scientific data to evaluate the safety and efficacy of the IMP, the sponsor designed the protocol in the manner that was not burdensome to the subjects: 1) Much of the data collected for secondary endpoints is derived from assessments performed for 'standard of care' visits; 2) Study visits are minimal (quarterly) with permissive visit windows (\pm 10 days); 3) Use of optional substudies for exploratory endpoints; and 4) Sponsor-provided Tyvaso to all subjects in the study.

Methods for handling missing data will be described in the sections discussing each outcome.

No imputation is planned for missing safety or exploratory data.

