6.8.1 Analysis of Pill Count Data

Coupled with the typical issues of lost and irretrievable IMP tablets, the protocol allowed that a subject could dose adjust during the study, a dose interruption could occur if medically warranted, and subjects were asked to remain on study (on or off IMP) pending adjudication of the primary clinical worsening event, pill count data will not provide an absolutely accurate compliance measurement. The following will be calculated:

- the number of tablets dispensed during the study (Baseline Visit through End of Study Visit)
- the number of tablets returned during the study
- the number of used tablets (calculated as tablets dispensed minus tablets returned)
- the duration of exposure (see Section 7.1)
- the number of expected pills taken at 15 µg and 30 µg QID
- percent of used tablets for number of expected pills for 15 µg and 30 µg QID overall and by 20% increments

Descriptive statistics will be presented by treatment group and subgroups, including, but not limited to, age, sex, racial, country, PAH etiology, background PAH therapy, background inhaled treprostinil, baseline WHO (see Sections 6.7.1 and 6.7.2).

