6.12 Primary Efficacy Analysis

As described in Section 2.1, the primary efficacy outcome is the TtCW, measured in days, where clinical worsening is defined as the first occurrence of any of the following:

- Death (all causes)
- Hospitalization due to worsening PAH
- Initiation of a parenteral (infusion or sub-cutaneous) prostacyclin directly related to worsening PAH
- Disease progression

- Unsatisfactory long-term clinical response

As described above, a blinded Event Adjudication Committee (EAC) will review all suspected clinical worsening events and make a final determination for each (see [Appendix 1](#)). The EAC Charter, Version [REDACTED], specifies evidence to be provided to the EAC along with the general rules and criteria for EAC confirmation of a primary endpoint of clinical worsening. Because the EAC Charter cannot address every possible scenario, the EAC Charter shall be viewed as a framework under which the EAC will operate. Each case will be determined on the basis of a consensus of the EAC, the members of whom are independent experts in PAH. Please see [Appendix 2](#) for general rules and criteria excerpted from the EAC Charter.

Subjects were not required to discontinue from the study after meeting a primary endpoint; thus, more than one clinical worsening event may be reported for the same subject. This section defines the calculation of time to each component of the primary outcome. The protocol specifies that investigators follow each subject for 30 days after the subject discontinues from the study to assess the occurrence of SAEs and for 90 days after the subject stops study medication for vital status. Further, the investigators are instructed to provide all clinical worsening events that occur after the primary clinical worsening event, as well as the vital status of all subjects at the time the sponsor terminates the study.

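### Protocol 7.10 ends participation at a confirmed worsening while other sections continue it to study close; following 7.10 would lose Week 24 and later-event data, more often on placebo if the drug works

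*Protocol*

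**What the plan says.** The documents give two rules for how long a subject stays in the study.

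**Participation ends at a confirmed event**
- Protocol 7.10.1: subjects "will continue their participation in the study until a clinical worsening event is confirmed by the EAC or the study is formally concluded".
- Protocol 7.10.2: "subjects are expected to continue their participation in the study until a clinical worsening event is confirmed by the EAC", or until the sponsor concludes the study.

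**Participation runs to study close**
- Protocol 2.1: "Subjects will continue participation in the study until it is formally concluded by the Sponsor". The synopsis says the same.
- Protocol 4.1: "Subjects will continue the study until it is formally concluded by the Sponsor".
- SAP 3.1 keeps subjects in until the sponsor concludes the study at 113 events.
- SAP 6.4.2: "All subjects were allowed to continue in the study until the close of study, whether on IMP or not". One of the listed exceptions is that "the subject met a primary endpoint and declined continuation in the study".
- SAP 6.12: "Subjects were not required to discontinue from the study after meeting a primary endpoint".

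The SAP is not uniform. Section 6.8.1 says that "subjects were asked to remain on study (on or off IMP) pending adjudication of the primary clinical worsening event", which is close to the 7.10 rule. Section 6.2 counts anyone with a worsening event as a completer, and 6.14.5 refers to subjects who leave on meeting the primary endpoint.

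Vital status has its own rule. Protocol 2.1 and 7.14 require it for every randomized subject at study conclusion. SAP 6.4.2 and 6.14.5 follow it to study close, as far as possible, in subjects who have left.

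**The concern.** The first-event primary needs nothing after the first event, but other planned analyses do.

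- **Week 24 endpoints.** Change in 6MWT and WHO class at Week 24 are two of the three Stage 2 endpoints (SAP 5.1.2 and 6.10.2). A subject who worsens early and then leaves has neither value.
- **Component incidence analyses (SAP 6.12.7).** These count component events that are not the first. Their censoring dates (SAP 6.12.1 to 6.12.5) run from the last study visit: 90 days beyond it for death, 30 days for hospitalization and parenteral prostacyclin, and none for the two walk-based components. An earlier last visit shortens every one of these windows.

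The missing subjects would be those who did worst. If the drug works, more of them would be on placebo.

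**Working it through.** **Inputs.** One-year worsening rates are 45% on placebo and 25% on active, with 120 per arm (SAP 4.1). Accrual is 1.5 years and total follow-up 2.5 years (Protocol 10.2; SAP 4.1). The alternative rates are 30% on placebo with a 13-point reduction, so 17% on active (Protocol 10.2). The documents give no figure for data lost after worsening.

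**Reproducing the design.** With exponential hazards h = −ln(1 − one-year rate):
- placebo −ln(0.55) = 0.598; active −ln(0.75) = 0.288; hazard ratio 0.481.
- Events (Schoenfeld) = 4(2.576 + 1.282)² / (ln 0.481)², about 112, against 113 stated.
- Power with 113 events is 90.5% at two-sided 0.01 and 97.3% at 0.05, against 90% and 97% stated.
- The exponential hazard-difference formula (Lachin-Foulkes, uniform accrual) gives 116 per arm, as stated.

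The hazards are therefore those behind the plan.

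**First events by Week 24.** Time = 24 × 7 / 365.25 = 0.460 years, and the proportion is 1 − exp(−h × time).
- Placebo: 1 − exp(−0.598 × 0.460) = 24.0%, or 28.8 of 120.
- Active: 1 − exp(−0.288 × 0.460) = 12.4%, or 14.9 of 120.
- Gap: 11.6 points, a ratio of about 2:1.

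**How far this could fall.** Under 7.10 a subject leaves at EAC confirmation, not at the event. The documents give no lag, so 4 and 8 weeks are assumptions. With a lag, only events in the first 20 or 16 weeks count.

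| Scenario | Placebo (of 120) | Active (of 120) |
|---|---|---|
| 45% v 25%, no lag | 29 | 15 |
| 45% v 25%, 4-week lag | 25 | 13 |
| 45% v 25%, 8-week lag | 20 | 10 |
| 30% v 17%, no lag (15.1% v 8.2%) | 18 | 10 |

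**First events by study close.** The proportion is 1 − [exp(−h × 1.0) − exp(−h × 2.5)] / (1.5h), which is 0.637 on placebo and 0.391 on active, or about 76 and 47 of 120. This is the number whose later component events would be exposed. It allows for no drop-out.

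**What imputation does.** SAP 6.13.3 imputes missing WHO class in both arms from placebo subjects, using baseline and Week 12 WHO class, 6MWT and Borg score. The worsening event is not among the listed predictors. SAP 6.13.1 gives subjects who stop study medication the placebo experience for 6MWT and leaves the program to an addendum. Under 7.10, the placebo subjects still observed at Week 24 would be mostly event-free. Early worseners would then be filled in largely from subjects who had not worsened. With about twice as many such subjects on placebo, this tends to flatter placebo and shrink the estimated difference.

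**The case against.** The protocol states the run-to-close rule in three places of its own. Its Section 7.14 encourages subjects to complete, and the reasons for withdrawal listed there (not a closed list) do not include a confirmed event. The End of Study triggers in the Schedule of Events do not name one either, and Section 8 has no exit procedure tied to one. SAP 6.12 records that leaving was not required and that investigators are told to report later worsening events. All of this stands as a reason not to presume that subjects were withdrawn. It does not settle the conflict. The contrary rule sits in the two sections that define the endpoints, three SAP sections allow for exit after an event, and the protocol text does not set out the instruction to report later events: 7.10.1 assesses worsening only up to the first.

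Stronger readings are tempting, and the documents do not support them.

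- **A reader might infer that mortality data are lost.** Vital status does not depend on participation. What remains is incomplete tracing, plus the death component of the incidence analysis, where SAP 6.12.1 censors at 90 days after the last visit even when a later death is known.
- **A reader might take 29 against 15 as the expected loss.** It is an upper bound. It ignores the confirmation lag. It includes deaths, which no further visit can recover and which already count as worsened for WHO class. It applies a constant hazard from randomization, although unsatisfactory long-term response needs at least 24 weeks of treatment. A progression first seen at Week 12 may be confirmed at the Week 24 visit itself, so that value may be observed.
- **A reader might infer that imputation ignores deterioration.** For WHO class it conditions on Week 12 values, so earlier decline is partly carried forward. The bias is reduced, not removed.
- **A reader might infer a risk to the primary or a false claim of benefit.** The primary uses first events only. With no treatment effect the imbalance disappears, and Stage 2 is tested only after a significant primary. The expected direction is against the sponsor's own effect.

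**Conclusion.** The contradiction is real and is not resolved elsewhere. If sites follow 7.10, Week 24 6MWT and WHO class are lost for subjects who worsen early, and later component events are lost from the SAP 6.12.7 analyses. At the planning rates the Week 24 exposure is at most about 24% of placebo and 12% of active subjects. The lag and lower-rate scenarios cut the counts, but the ratio stays near 2:1. The unequal loss rests on two conditions: sites act on 7.10, and the drug works roughly as planned. The likely effect is a diluted key secondary result. The primary is unaffected, and total mortality is largely protected.

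**What to change.** Reconcile Protocol 7.10.1 and 7.10.2 with Protocol 2.1 and 4.1 and with SAP 6.4.2 and 6.12. State that scheduled outcome assessments and reporting of worsening events continue after an EAC-confirmed event until study conclusion, whatever the study-drug status. Bring the exit wording in SAP 6.2, 6.8.1 and 6.14.5 into line.

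Collecting the data is not enough. Protocol 10.3 limits efficacy summaries to evaluations up to the last study visit or 30 days after permanent discontinuation of study drug, and sends anything further to listings. The SAP says that it supersedes the protocol's statistical section but does not say whether this cut-off lapses. Align 10.3, or say so in the SAP, so that the analyses use the additional data.

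This concerns data collection only, not treatment. The cost is a protocol clarification, a line in the SAP and some extra visits by subjects who have already had an event.

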7.10.2 Clinical Failure

Clinical failure will be assessed from randomization to the first of the following events:

- Meets primary endpoint definition of clinical worsening, as confirmed by EAC, or
- Receives randomized treatment for at least 24 weeks and has:
 - Lack of sustained improvement from Baseline WHO Functional Class: defined by two consecutive visits of no sustained improvement from Baseline WHO FC, visits may be scheduled or unscheduled; and
 - Lack of sustained improvement from Baseline 6MWD (average at Baseline): defined by two consecutive visits of no sustained improvement from Baseline 6MWD (≤ 0 meters or too ill to walk, directly related to PAH), visits may be scheduled or unscheduled.

The Sponsor will derive the composite measures of clinical failure and TtCF from the data collected per the protocol. Unlike clinical worsening, neither a specific Investigator's assessment for clinical failure nor an EAC confirmation of suspected events will occur.

As above, subjects are expected to continue their participation in the study until a clinical worsening event is confirmed by the EAC or the study is formally concluded by the Sponsor.

7.10.3 Six Minute Walk Test

The 6MWT, which is designed to evaluate exercise capacity associated with carrying out activities of daily living, will be performed to evaluate potential treatment effects on exercise capacity at all scheduled study visits: Screening, Baseline (two 6MWTs, taken on consecutive days, before the start of study drug dosing), Weeks 4, 8, 12, Quarterly Visits and at the End of Study Visit. At the Screening Visit, the 6MWT should be measured within 1-2 hours, ± 15

minutes, after second or third dose of inhaled treprostinil or approximately 4-6 hours, ± 15 minutes, after waking if the subject has not begun inhaled treprostinil treatment yet. At both days of the Baseline Visit (Days 1 and 2), the 6MWT should be measured within 1 hour, ± 15 minutes, before the second or third dose of inhaled treprostinil. At all subsequent visits, e.g. Week 4 and beyond, the 6MWT should be measured within 1-2 hours, ± 15 minutes, after second or third dose of inhaled treprostinil. At all subsequent visits, e.g. Week 4 and beyond, the 6MWT should be measured within 1-2 hours, ± 15 minutes, after second or third dose of inhaled treprostinil and study drug combined. Appendix 3 presents the standardized procedures for administration of the 6MWT.

At any point in the trial, if a subject is assessed for the 6MWT while using oxygen therapy then all future 6MWTs should be conducted with the same oxygen flow.

7.10.4 Borg Dyspnea Score

The modified 0–10 category-ratio Borg scale consists of an 11-point scale with which the subjects rate the maximum level of dyspnea they experienced during the 6MWT. Scores range from 0 (for the best condition) and 10 (for the worst condition) with nonlinear spacing of verbal descriptors of severity corresponding to specific numbers. Subject may choose the number or the verbal descriptor to reflect presumed ratio properties of sensation or symptom intensity. Appendix 4 presents the standardized administration details for the Borg Dyspnea Score procedures the clinical site personnel should use. Each subject will provide a rating of dyspnea immediately following the 6MWT.

7.10.5 WHO Functional Class

At the Screening Visit the Investigator will classify the subjects for PAH severity using the World Health Organization (WHO) Functional Class. Assessment for WHO Functional Classification for PAH should be made at Screening, Baseline, Week 4, Week 8, Week 12 (first Quarterly Visit), at Quarterly Follow-up Visits and at the End of Study Visit. See Appendix 5 for categories.

7.10.6 NT-pro-BNP

Blood samples to be used for Plasma N-terminal pro-Brain Natriuretic Peptide (NT-pro-BNP; a biomarker of congestive heart failure) measurement will be collected at Screening, Baseline, Week 4, Week 8, Week 12 (first Quarterly Visit), at Quarterly Follow-up Visits, and at the End of Study Visit.

